### **Statistical analysis:**

The SPSS computer software (IBM SPSS Statistics v21.0; IBM Corp., USA) was utilized for the statistical analysis of the collected data in this study. The significance of the conducted statistical results was considered at two tailed  $\alpha$  of .05. Normal distribution of the data was tested utilizing the Shapiro-Wilk test and the skewness test considering skewness z-score threshold values range from -3.29 to +3.29. All the continuous variables were not normally distributed, except for age and OHIP scores before treatment. Descriptive statistics for normally distributed continuous variables (age and OHIP scores before treatment) included the mean, standard error, standard deviation, median, maximum value, minimum value, and confidence intervals. Meanwhile, descriptive statistics for the non-normally distributed continuous variables included the mean, standard deviation, median, interquartile range, minimum value, and maximum value. Categorical variables in this study (presence of redness, erosion, keratosis, ulceration, and denture fissuratum) were presented as frequencies and percentages.

The Wilcoxon Signed Ranks test was used to test paired differences in satisfaction ratings, dentist's evaluations, and OHIP-EDENT scores after using carved and non-carved lower dentures. The Mann Whitney U test was utilized to identify differences in satisfaction ratings, dentist's evaluations, and OHIP-EDENT scores between genders. Spearman's Rho rank correlations were used to identify the correlations between satisfaction ratings, dentist's evaluations, and OHIP-EDENT scores. Associations between identification of lesions following denture use (presence of redness, erosion, keratosis, ulceration, and denture fissuratum) and having the retromolar pad area of the lower denture carved or not were tested via Fisher's Exact test.

The multiple linear regression analysis was used to identify the contribution of having the retromolar pad area carved or not, satisfaction ratings, and dentist evaluation towards the prediction of OHIP-EDENT scores considering the confounding effects of gender and age.

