Table 5 presents correlations between age, patient satisfaction, and OHIP scores. The results show that older patients were more comfortable with upper dentures than younger patients (Spearman Rho= 0.309,  $P= .031$ , Table 5). Also, higher pain scores were associated with higher OHIP scores (i.e. worse impacts) after using carved ( $P= .001$ ) and non-carved ( $P< .001$ ) lower dentures (Table 5). In addition, lower OHIP scores (i.e. better impacts) were associated with higher satisfaction with retention at rest, retention at function, denture comfort, general satisfaction with dentures, retention during eating, and retention during speaking after using carved or non-carved lower dentures ( $P< .05$ , Table 5). Besides, correlations between age and dentist rating of dentures showed that older participants were found to have better dentist ratings of retention (Sperman Rho= 0.402,  $P= .004$ ) and higher stability (Spearman Rho= 0.402,  $P= .003$ ) of upper dentures than younger participants.

A multiple linear regression analysis was used to identify the contribution of having the retromolar pad area carved or not, satisfaction ratings, and dentist evaluation of dentures towards the prediction of OHIP scores considering the confounding effects of gender and age (Table 6). Being a female, having lower dentist ratings of denture esthetics, and having more pain due to lower dentures were associated with higher scores of OHIP indicating worse oral health impacts

of the prosthesis ( $P < .05$ , Table 6). Being a female was associated with an increase of OHIP scores by 4 units ( $P = .007$ ). Also, for each decreased unit of dentist ratings of denture esthetics, the OHIP scores were increased by 2 units ( $P = .018$ ). Furthermore, for each increased unit of pain levels due to lower dentures, the OHIP scores were increased by 0.7 units ( $P = .020$ ) (Table 6).

Further multiple linear regression analyses were conducted to identify the contribution of having the retromolar pad area carved or not and dentist evaluation of dentures towards the prediction of patient satisfaction with different denture aspects considering the confounding effects of gender and age (Table 7). The results showed that carved lower dentures were associated with 1.144 times higher satisfaction with lower denture retention during function ( $P = .040$ , Table 7). **[name] please note that Being carved or not was significant predictor for retention of the denture during function.**

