Besides, patients satisfaction with lower denture retention at rest was decreased by 0.053 unit for each year increase in the age ( $P = .027$ , Table 7). Also, being a female was associated with higher patient satisfaction with lower denture retention at rest ( $B = 0.970$ ,  $P = .033$ ), lower denture retention at function ( $B = 1.404$ ,  $P = .027$ ), lower denture comfort ( $B = 1.374$ ,  $P = .007$ ), general satisfaction with upper and lower dentures ( $B = 1.361$ ,  $P = .002$ ), and retention of upper and lower dentures during eating ( $B = 0.978$ ,  $P = .036$ ) (Table 7).

In addition, higher levels of perceived pain due to lower dentures were associated with lower levels of satisfaction with lower denture retention at rest ( $B = -0.184$ ,  $P = .032$ ), lower denture retention at function ( $B = -0.365$ ,  $P = .002$ ), lower denture comfort ( $B = -0.440$ ,  $P < .001$ ), general satisfaction with upper and lower dentures ( $B = -0.254$ ,  $P = .002$ ), retention of upper and lower dentures during eating ( $B = -0.320$ ,  $P < .001$ ), and retention of upper and lower dentures during

speaking ( $B = -0.235$ ,  $P = .005$ ) (Table 7). Furthermore, higher dentist ratings of lower denture stability (**[name] please note for the discussion that this could be explained by that stability is related to each of retention, support and occlusion**) was associated with higher patient satisfaction with lower denture retention at rest ( $B = 0.527$ ,  $P = .037$ ), lower denture retention at function ( $B = 0.958$ ,  $P = .005$ ), and lower denture comfort ( $B = 0.723$ ,  $P = .011$ ) (Table 7).

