	Patient satisfaction with retention of upper and lower dentures during eating	-.207	.504	-.061	-.411	.682	-1.211	.796
	Patient satisfaction with smile and appearance of upper and lower dentures	-1.720	.888	-.188	-1.937	.056	-3.488	.047
	Patient satisfaction with retention of upper and lower dentures during speaking	-.653	.366	-.177	-1.787	.078	-1.381	.074

R^2= Coefficient of determination, DW= Durbin Watson statistic, Unst Co= Unstandardized coefficient, St Co= Standardized coefficient, B= Beta statistics, SE= Standard Error, t= t statistics, P= Two tailed probability value, CI= Confidence intervals. \*Gender, age, having the lower denture carved or not, and dentist ratings of lower dentures, and patient satisfaction with dentures were entered in the regression model.

**Table 7.** Linear regression analyses to predict patient satisfaction with different denture aspects utilizing the demographic variables, having the lower denture carved or not, and dentist ratings of lower dentures among the study sample (n= 50).

Dependent variable	Predictors*	Unst Co		St Co	t	P	95% CI for B	
		B	SE	Beta			Lower Bound	Upper Bound
Patient satisfaction with lower denture retention at rest R  = .295 DW=2.000	Constant	6.768	3.155	---	2.145	.035	.499	13.038
	Gender	.970	.449	.222	2.163	.033	.079	1.862
	Age	-.058	.026	-.211	-2.242	.027	-.109	-.007
	Carved denture or not	.338	.395	.078	.856	.394	-.447	1.124
	Dentist rated lower denture retention	-.170	.164	-.151	-1.035	.303	-.495	.156
	Dentist rated lower denture stability	.527	.249	.373	2.114	.037	.032	1.022
	Dentist rated lower denture support	.080	.264	.038	.301	.764	-.446	.605
	Dentist rated lower denture esthetics	-.021	.273	-.008	-.075	.940	-.564	.523
	Perceived pain due to lower denture	-.184	.084	-.216	-2.184	.032	-.351	-.017
Patient satisfaction with lower denture retention at function R  = .309 DW=1.728	Constant	4.512	4.410	---	1.023	.309	-4.249	13.273
	Gender	1.404	.624	.238	2.251	.027	.165	2.643
	Age	-.031	.036	-.084	-.864	.390	-.103	.041
	Carved denture or not	1.144	.549	.195	2.085	.040	.054	2.235
	Dentist rated lower denture retention	-.266	.229	-.175	-1.158	.250	-.722	.190
	Dentist rated lower denture stability	.958	.335	.504	2.858	.005	.292	1.623
	Dentist rated lower denture support	-.166	.371	-.059	-.446	.657	-.904	.572
	Dentist rated lower denture esthetics	-.431	.382	-.125	-1.128	.262	-1.189	.328

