	Dentist rated lower denture retention	-.166	.168	-.151	-.987	.326	-.499	.168
	Dentist rated lower denture stability	.101	.255	.074	.397	.693	-.406	.609
	Dentist rated lower denture support	.111	.271	.054	.410	.683	-.427	.650
	Dentist rated lower denture esthetics	-.209	.280	-.084	-.745	.458	-.766	.348
	Perceived pain due to lower denture	-.320	.086	-.386	-3.713	<.001	-.491	-.149

	denture							
Patient satisfaction with smile and appearance of upper and lower dentures R  = .092 DW=1.959	Constant	9.960	1.298	---	7.676	<.001	7.382	12.539
	Gender	.235	.184	.149	1.275	.206	-.131	.602
	Age	-.009	.011	-.091	-.856	.394	-.030	.012
	Carved denture or not	.014	.163	.009	.088	.930	-.309	.337
	Dentist rated lower denture retention	-.085	.067	-.209	-1.264	.210	-.219	.049
	Dentist rated lower denture stability	.078	.102	.153	.761	.449	-.126	.282
	Dentist rated lower denture support	-.112	.109	-.147	-1.027	.307	-.328	.104
	Dentist rated lower denture esthetics	.115	.112	.124	1.021	.310	-.109	.338
	Perceived pain due to lower denture	-.067	.035	-.219	-1.952	.054	-.136	.001
	Constant	12.767	3.044	---	4.194	<.001	6.718	18.816
Patient satisfaction with retention of upper and lower dentures during speaking R  = .185 DW=2.367	Gender	.702	.433	.179	1.623	.108	-.158	1.562
	Age	-.019	.025	-.076	-.754	.453	-.068	.031
	Carved denture or not	-.280	.381	-.072	-.735	.464	-1.038	.477
	Dentist rated lower denture retention	-.009	.158	-.009	-.055	.957	-.323	.305
	Dentist rated lower denture stability	.254	.240	.201	1.056	.294	-.224	.731
	Dentist rated lower denture support	-.074	.255	-.039	-.290	.773	-.581	.433
	Dentist rated lower denture esthetics	-.462	.264	-.202	-1.752	.083	-.986	.062
	Perceived pain due to lower denture	-.235	.081	-.309	-2.903	.005	-.397	-.074
	Constant	12.767	3.044	---	4.194	<.001	6.718	18.816
	Gender	.702	.433	.179	1.623	.108	-.158	1.562

R^2= Coefficient of determination, DW= Durbin Watson statistic, Unst Co= Unstandardized coefficient, St Co= Standardized coefficient, B= Beta statistics, SE= Standard Error, t= t statistics, P= Two tailed probability value, CI= Confidence intervals. \*Gender, age, having the lower denture carved or not, and dentist ratings of lower dentures were entered in the regression model.

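### Table 7's retention-at-function block mixes two regression fits, so its carving result (1.144, P=.040) does not belong to the model printed; the other carving and gender coefficients are conditional associations

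*SAP*

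**What the plan says.** The Statistical analysis section uses the Wilcoxon signed ranks test to "test paired differences in satisfaction ratings, dentist's evaluations, and OHIP-EDENT scores after using carved and non-carved lower dentures". It then plans a multiple linear regression for the contribution of carving, "satisfaction ratings, and dentist evaluation towards the prediction of OHIP-EDENT scores considering the confounding effects of gender and age". Only gender and age are called confounders.

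The Table 6 footnote (OHIP) names the two demographic variables first and then says: "having the lower denture carved or not, and dentist ratings of lower dentures, and patient satisfaction with dentures were entered in the regression model". The rows show four dentist ratings and nine patient ratings.

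For Table 7 the Results give the aim as to "identify the contribution of having the retromolar pad area carved or not and dentist evaluation of dentures" in predicting satisfaction. The title says the models "predict patient satisfaction with different denture aspects utilizing the demographic variables, having the lower denture carved or not, and dentist ratings of lower dentures", and the footnote again puts the demographic variables first and then says: "having the lower denture carved or not, and dentist ratings of lower dentures were entered in the regression model". None of these names pain. Yet all eight blocks print a pain row, and the Results interpret it, for example that "higher levels of perceived pain due to lower dentures were associated with lower levels of satisfaction with lower denture retention at rest".

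For retention at function the Results report that "carved lower dentures were associated with 1.144 times higher satisfaction with lower denture retention during function" (P=.040; as a linear coefficient this is a difference of 1.144 points, not a ratio). They single carving out as a significant predictor. The same block's pain coefficient (-0.365, P=.002) is reported as coming from the same table.

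**The concern.** A regression block printed with one R² should be one fit. If its rows come from two, neither the carving coefficient nor the pain coefficient can be read as adjusted for the other. This is the one block in Tables 6 and 7 where carving reaches significance.

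The second issue is what the coefficients mean. Carving may change the ratings given after wearing a denture, and the plan tests those ratings as outcomes of carving. Holding them fixed removes whatever part of the carving difference they carry. Tables 6 and 7 are also the only places where carving estimates have intervals, so a reader may take them as the effect of carving. The same applies to gender: the Results report about 4 more OHIP units for females without saying that this compares women and men at equal ratings.

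**Working it through.** **Inputs.** Coefficients, SEs, R² and intervals come from Tables 6 and 7, means and SDs from Table 1, and gender means from Table 4. The number of records per denture is taken as 49 (Table 2 frequencies, e.g. 40+9). Females are taken as 22, inferred as 49 minus 27; the Results text prints 23, and the table titles say 50.

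**1. Carving identity.** The same people wore both dentures, so gender and age are balanced. Least squares then requires: raw carved minus non-carved mean = B(carving) + Σ B(rating) × Table 1 difference. The differences are retention 0.32, stability 0.27, support 0.27, esthetics 0.03 and pain -0.88.

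| Table 7 block | Sum with pain | Raw |
|---|---|---|
| Rest | .609 | .61 |
| Comfort | .814 | .82 |
| Insertion | -.081 | -.08 |
| General | .489 | .49 |
| Eating | .733 | .73 |
| Smile | .040 | .04 |
| Speaking | -.041 | -.04 |
| **Function** | **1.581** | **1.26** |

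For function, the dentist ratings contribute -.085+.259-.045-.013 = .116, and pain contributes -.365×-.88 = .321. Without pain, 1.144+.116 = 1.260, which equals the raw 1.26.

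**2. Outcome mean.** The constant plus Σ B × predictor mean should equal the outcome mean. Gender and carving are coded 1/2, inferred because that closes the other blocks. Function gives 6.37 with pain and 6.97 without, against (6.33+7.59)/2 = 6.96. The other seven blocks close within 0.04 with pain.

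**3. Gender identity.** B(gender) + B(age)×3.88 + Σ B(rating) × mean female-male gap should equal the raw gap. Function gives 1.374 with pain and 1.522 without, against (2.22+0.83)/2 = 1.525. The other seven close within 0.01 with pain.

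**4. Degrees of freedom.** The function constant's CI half-width is (13.273+4.249)/2 = 8.761, and 8.761/4.410 = 1.98662 (1.98628 to 1.98696 over rounding). This admits t with 90 df (1.98667) and excludes 89 df (1.98698). The other seven blocks admit 89.

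**5. Standard errors.** With the same predictors, SEs scale with residual SD.
- Total SS = 48(SD₁²+SD₂²) + 98(difference/2)²: function 841.5, comfort 671.7.
- Residual SDs on 89 df: √(.691×841.5/89) = 2.556 and √(.606×671.7/89) = 2.139, ratio 1.195.
- Expected function SEs from the comfort block: pain .094×1.195 = .112 (printed .112); carving .441×1.195 = .527 (printed .549).

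So the pain row and R² belong to the with-pain fit, and the carving row does not.

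**6. Carving with pain included.** Let δ be the adjusted carving-pain slope. Then B(with pain) = 1.144 + .365δ.
- Pain-free R² ≈ .309 - 3.251²×.691/89 = .227, giving a residual SD of √(.773×841.5/90) = 2.689.
- SE²/residual variance for carving is .0426 with pain (from comfort) and .0417 without. The unrounded gap is .000913.
- This gap equals δ²/SSp, where SSp, the residual sum of squares of pain given the other predictors, is about 518. So |δ| ≈ √.473 = .69.
- If δ is negative, B ≈ 1.144-.251 = 0.89, SE .528, P about .09. Allowing for rounding, B is about 0.85 to 0.92 and P about .08 to .11.
- If δ is positive, B is about 1.37 to 1.44 and P about .01.
- P exceeds .05 once δ is below about -0.27. The raw pain difference is -0.88.

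**7. Size of the conditioning.** In Table 6 the 13 ratings contribute -1.343, and -1.324-1.343 = -2.667 against the raw 8.45-11.12 = -2.67. The reduction against raw is:
- OHIP 50%
- comfort 50% (.412 v .82)
- rest 45% (.338 v .61)
- eating 38% (.454 v .73)
- general satisfaction 34% (.323 v .49)

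Insertion (-.072 v -.08), smile (.014 v .04) and speaking (-.280 v -.04) have near-zero raw differences and show no common direction.

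**8. Gender on OHIP.** Table 4 gaps are 0.11 (P=.538) and 1.49 (P=.959), mean 0.80. Removing dentist ratings (1.381), patient ratings (1.352) and age (0.512) from 4.063 leaves 0.82. With n=27 and 22, the arm SEs are 2.34 and 1.94. The mean gap then has SE 1.52 to 2.14 as the unknown within-person correlation runs from 0 to 1, so its 95% CI runs from -2.3 to 3.9 up to -3.5 to 5.1.

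**The case against.** The plan frames these models as prediction, the table titles do the same, and most sentences speak of association. The planned carving comparison is already the paired Wilcoxon test. A gender coefficient at equal ratings is a legitimate conditional quantity, and Table 4's rank tests per denture are not the same analysis as a pooled mean model. Pain is visible in every Table 7 block, so its absence from title and footnote is editorial. All of this stands, and it makes the adjustment and pain-listing points secondary. It does not answer the mixed block, which is an arithmetic inconsistency whatever the aim of the model.

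A reader might infer more than the document supports:
- *Carving does not help retention at function.* Not supported: the paired test gives P=.002 and uses neither pain nor dentist ratings. Only the regression corroboration is in doubt.
- *Carving is certainly non-significant once pain is included.* Not supported: the printed figures fix the value only up to the sign of δ.
- *Adjustment made the OHIP result non-significant.* Not supported: the paired P is already .055, and the Results do not interpret the OHIP carving coefficient.
- *Every carving estimate is attenuated.* Not supported: three items show no common direction. For general satisfaction, Table 1 prints no paired P for comparison.

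**Conclusion.** The retention-at-function block is wrong as printed. Three identities and the degrees of freedom point to a pain-free fit for the constant, carving, gender and dentist-rating rows; the standard errors place the pain row and R²=.309 in a fit with pain. The gaps of 0.32 on the carving identity and 0.59 on the outcome mean exceed anything rounding could produce. The figures 1.144 and P=.040 should not be cited as a result of the model shown. The likely with-pain value is near 0.89 with P about .09, on the assumption that δ is negative.

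Of lesser weight, the remaining carving and gender coefficients in Tables 6 and 7 are associations at fixed post-wear ratings, not total effects. The largest consequence for the text is the gender statement on OHIP: 4.063 conditional against 0.80 unadjusted. The conclusions rest on 49 records per denture and, for the gender and outcome-mean checks, on 22 females; the outcome-mean check also rests on 1/2 coding. These choices close the other blocks.

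**What to change.** - Re-run the retention-at-function block with one stated predictor set, and correct the carving coefficient, its P value and R² in Table 7 and the Results.
- Name pain as a predictor in the Results text, the Table 7 title and its footnote.
- For OHIP and each satisfaction item, estimate carving from a within-participant model (participant as random effect, with period and sequence) without post-wear ratings. Report it with a 95% CI beside the Wilcoxon result.
- Label Tables 6 and 7 as exploratory conditional associations, and do not read their carving or gender coefficients as effects.
- For gender and OHIP, give the unadjusted or age-adjusted difference first.

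The cost is one re-run block, one small model per outcome and some rewording. The regression result for carving may turn out less favourable than the one now printed.

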The calculated sample size was 46 participants. A priori power analysis based on linear multiple regression test (G\*Power, version 3.1.9.7; Heinrich-Heine University) calculated the minimum sample size to be 46 participants. The calculation considered a significance level ( $\alpha$ ) of .05, a statistic power ( $1 - \beta$ ) of 0.8, and an effect size of 0.3. Extra participants were recruited to balance for participant drop outs and secure the required minimum sample size. Fifty participants were recruited for the study, and none of participants was lost during the investigation (drop out ratio was 0%). Therefore, 50 participants were finally recruited and completed the study, and had their data collected and analyzed.

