## Results

The data was collected from a total of 49 participants (23 females and 27 males), and was then processed and analyzed. Participants age ranged from 40 to 78 years old (mean age= 62.8 years old, SD= 8.01, SE= 1.145, median= 63.0, 95% CI= 60.51 – 65.12).

Table 1 demonstrates the descriptive statistics for continuous variables in this study including dentist evaluations of dentures, patients' satisfaction with dentures, and OHIP-EDENT scores among the participants of this study. Paired comparisons of carved and non-carved lower dentures showed that patient satisfaction with retention at function ( $P= .002$ ) and comfort during the use of carved lower dentures ( $P= .026$ ) were significantly higher than non-carved lower dentures (Table 1). Furthermore, the patients demonstrated a tendency to be more satisfied with denture retention at rest as well as during eating when used carved lower dentures in comparison to non-carved ones. This difference was not significant but was close to be significant ( $P= .052$ ,

Table 1). In addition, carved lower dentures were associated with lower OHIP scores (better impacts on oral health) than the non-carved lower dentures; however, the difference was not significant ( $P= .055$ , Table 1). Nevertheless, this tendency was confirmed by the Mann Whitney U test as a significant difference was found in the OHIP scores between carved and non-carved lower dentures ( $MWU= 887.0$ ,  $Z= -2.241$ ,  $P= .025$ ). The carved lower dentures were associated with lower OHIP scores indicating better impacts on oral health than the non-carved dentures.

Table 2 presents the distribution (frequencies and percentages) of redness, erosion, keratosis, ulceration, and denture fissuratum following the use of the tested complete denture designs during this study. Redness was the most observed mucosal change, 18.4% with non-carved dentures and 12.2% with carved dentures. No significant differences in mucosal changes were observed between carved and non-carved lower dentures ( $P> .05$ , Table 2).

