General satisfaction with upper and carved lower dentures	Rho	.058	-.316	-.491
	P	.695	.027	<.001
Retention during eating with upper and non carved lower dentures	Rho	.260	-.582	-.032
	P	.072	<.001	.828
Retention during eating with upper and carved lower dentures	Rho	-.069	-.320	-.459
	P	.639	.025	.001
Smile and appearance of upper and	Rho	-.102	-.290	-.196

non carved lower dentures	P	.484	.043	.177
Smile and appearance of upper and carved lower dentures	Rho	.181	-.359	-.207
	P	.213	.011	.153
Retention during speaking with upper and non carved lower dentures	Rho	.066	-.435	-.145
	P	.655	.002	.321
Retention during speaking with upper and carved lower dentures	Rho	-.016	-.276	-.505
	P	.911	.055	<.001
OHIP score before treatment	Rho	-.104	.253	-.052
	P	.479	.079	.722

NCLD= Non-carved lower denture, CLD= Carved lower denture, OHIP= Oral Health Impact Profile – 14, Rho= Spearman correlation coefficient, P= Two tailed probability value.

**Table 6.** Linear regression analyses to predict OHIP scores after treatment utilizing the demographic variables, having the lower denture carved or not, dentist ratings of lower dentures, and patient satisfaction with dentures among the study sample (n= 50).

Dependent variable	Predictors*	Unst Co		St Co	t	P	95% CI for B	
		B	SE	Beta			Lower Bound	Upper Bound
OHIP scores after treatment R  = .468 DW = 1.837	Constant	63.274	13.648	---	4.636	<.001	36.118	90.430
	Gender	4.063	1.465	.281	2.774	.007	1.149	6.977
	Age	-.132	.080	-.146	-1.645	.104	-.292	.028
	Carved denture or not	-1.324	1.222	-.092	-1.084	.282	-3.755	1.107
	Dentist rated lower denture retention	.314	.507	.084	.619	.538	-.695	1.323
	Dentist rated lower denture stability	-.704	.793	-.151	-.888	.377	-2.282	.873
	Dentist rated lower denture support	.477	.833	.069	.572	.569	-1.182	2.135
	Dentist rated lower denture esthetics	-2.070	.860	-.245	-2.408	.018	-3.780	-.359
	Perceived pain due to lower denture	.711	.299	.253	2.374	.020	.115	1.306
	Patient satisfaction with lower denture retention at rest	-.213	.473	-.064	-.451	.653	-1.154	.727
	Patient satisfaction with lower denture retention at function	-.281	.400	-.115	-.704	.484	-1.077	.514
	Patient satisfaction with lower denture Comfort	.090	.522	.033	.173	.863	-.948	1.128
	Patient satisfaction with easiness of lower denture insertion	-.359	.473	-.068	-.758	.450	-1.300	.583
	Patient general satisfaction with upper and lower dentures	-.244	.518	-.066	-.471	.639	-1.275	.787

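### Does the 80% power behind the 46 participants, taken from a multiple-regression calculation, leave the carved versus non-carved comparison without support?

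*SAP*

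**What the plan says.** The sample-size paragraph under the Statistical analysis heading describes an "A priori power analysis based on linear multiple regression test" which "calculated the minimum sample size to be 46 participants", with alpha .05, power 0.8 and effect size 0.3. It adds that "Extra participants were recruited to balance for participant drop outs and secure the required minimum sample size", and that 50 were recruited. It does not say whether the test was of the overall R², of an increase in R² or of one coefficient. The tested and total predictors, and whether 0.3 is f² or R², are also not given.

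The methods text under the same heading gives the treatment contrast to another test: "The Wilcoxon Signed Ranks test was used to test paired differences in satisfaction ratings", and likewise in dentist ratings and OHIP-EDENT scores. Regression has a separate task, the contribution of carving, "satisfaction ratings, and dentist evaluation towards the prediction of OHIP-EDENT scores considering the confounding effects of gender and age". Table 6 enters 16 predictors: gender, age, carving, four dentist ratings, pain and eight patient satisfaction items.

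**The concern.** In a cross-over trial a reader will take the stated 80% as the power of the within-person comparison of the two dentures. Here it belongs to a different family of tests. The SAP also reports that "All the continuous variables were not normally distributed, except for age and OHIP scores before treatment", so the signed-rank test carries the comparison, and no detectable difference is attached to it. The Results then describe retention at rest and during eating (both P = .052) with the words "This difference was not significant but was close to be significant" and treat OHIP (P = .055) as a tendency. Readers get no help in telling no effect from an effect too small to detect.

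The regression side looks weak too. If the 80% was meant for the whole OHIP model, 46 independent observations would be well short. At stake would be a sample size presented as adequate for tests it was never calculated for.

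**Working it through.** **Inputs.** From the sample-size paragraph: N = 46, alpha .05, power 0.8, effect size 0.3. From Table 6: 16 predictors, with standard errors and confidence limits. From Table 2: 49 persons per denture. Assumptions: a fixed-model regression test, and 0.3 read either as f² or as (partial) R², in which case f² = 0.3/0.7 = 0.4286.

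**Step 1: can 46 be reproduced?** For q tested predictors among p in total, power = 1 − F(crit; q, N − p − 1, λ), with noncentrality λ = f² × N. Searching every q ≤ p ≤ 16 for a required N of exactly 46:

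- 0.3 as f²: 4 tested of 6, 7, 8, 9, 10, 11 or 12 (7 set-ups). For 4 of 8, power is .796 at 45 and .808 at 46.
- 0.3 as R²: 9 of 9 (.791, then .804), 9 of 10, 8 of 15, and 8 of 16 (.795, then .809) (4 set-ups).

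So 7 + 4 = 11 set-ups give 46. Two of them match blocks in the SAP's own models: 8 of 16 fits the eight satisfaction items of Table 6, and 4 of 8 fits the four dentist ratings in the eight-predictor models of Table 7. The four dentist ratings within Table 6 (4 of 16, f² = 0.3) need 47, with .792 at 46. This does not show which test was run. It shows that 46 is a plausible output.

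**Step 2: other readings of the OHIP model, on 46 independent units.**

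| Test | Power at 46, f² / R² | N needed, f² / R² |
|---|---|---|
| All 16 predictors | .420 / .600 | 79 / 60 |
| 14 beyond gender and age | .460 / .646 | 75 / 57 |
| Carving coefficient alone | .948 / .990 | 31 / 25 |

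The two large joint tests fall short, and the coefficient of interest does not.

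**Step 3: how many rows did the model use?** Interval half-width divided by SE in Table 6:

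- constant: (90.430 − 36.118)/2/13.648 = 1.9897
- gender: (6.977 − 1.149)/2/1.465 = 1.9891
- carving: (1.107 + 3.755)/2/1.222 = 1.9894

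The .975 quantile of t is 1.9897 on 81 df and 2.037 on 32 df. Since 81 = 98 − 17, the model was fitted on about 98 rows, two per person, and not on 49.

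**Step 4: power on two rows per person.** Treated as independent, 92 rows (46 × 2) give .889 / .979 for all 16 predictors and .911 / .985 for the 14. For all 16, 98 rows give .916 / .987. The rows are paired, so these figures are nominal. Carving varies within a person, and positive within-person correlation sharpens that contrast, so a single penalty factor on the whole model would be wrong. A simulation of 46 people with two rows each (f² = 0.3, equal effects, a correlation-aware overall test, 1,500 runs) gave power of .85 to .93 at residual correlations of .3 and .5 when the ratings' own within-person correlation was .2 to .5. It gave .81 and .79 when that correlation was .8.

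**Step 5: the paired test.** Using the noncentral t with signed-rank efficiency 3/π and two-sided .05, 80% power is reached at 0.43 SD of the paired differences with 46 pairs, 0.42 with 49 and 0.41 with 50. This assumes normal differences without ties. If 0.3 were read as a standardised paired difference, power at 46 would be about 49%. The SAP does not say that 0.3 is such a difference, so this is not a shortfall against its own target.

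**The case for a change.** The strongest case for a change is that this is more than detail left to a protocol. The SAP chose to state a calculation, called its result the required minimum, and based it on a test other than the one used for the main comparison. A few words would prevent a misreading: name the sub-test, predictors and metric, say that the 80% was not calculated for the paired comparison, and give a detectable paired difference.

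The description of the gap stands: the settings are unstated, and the 80% is not the power of the signed-rank test. The consequence does not follow. The sentence claims power only for a regression test, and nothing in the SAP contradicts that. A detectable difference added now would be worked out after the data were seen; a paired estimate with its confidence interval would serve the reader better, and that is a reporting question. The Results already call the .052 and .055 findings not significant, so the sample-size wording does not turn them into positive claims. Whether to speak of tendencies is also a reporting matter.

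**Conclusion.** No change to the plan. The sample-size paragraph lacks detail, but no stated figure is shown to be wrong. The 46 is reproduced by 11 ordinary set-ups, one of which fits the satisfaction block of Table 6. The low figures of 42% to 65% apply only if the whole 16-predictor model, or its 14-predictor block, was the target and each person gave one row. The fitted model had about 98 rows, where nominal power for all 16 predictors is 92% or 99%, and the simulation at f² = 0.3 stayed at about 80% or above. For the carving coefficient alone, 46 exceeds the 31 needed at f² = 0.3.

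For the paired contrast no target effect is set, so neither adequacy nor shortfall can be shown; about 0.42 SD is detectable with 49 pairs. These conclusions rest on the fixed-model formula, on reading 0.3 as f² or R², and on 49 pairs from the Table 2 counts (the sample-size paragraph gives 50, which moves the detectable difference only to 0.41 SD). Enrolment is closed and the analyses are run, so writing down the settings would change no estimate, P value or conclusion.
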